10. STATISTICAL EVALUATION

10.1 General Comments

Summary tables (descriptive statistics and/or frequency tables) will be provided for baseline variables, PK variables, and safety variables. In general, continuous variables will be described by descriptive statistics (mean, median, standard deviation, minimum, and maximum). Frequency counts and percentage of subjects within each category will be provided for categorical data.

10.2 Subject Disposition

Subject disposition will be summarized by showing the number of subjects screened, and the number and percent of screen failures and enrolled subjects; the number and percent of subjects completed and discontinued, overall and by treatment, along with the primary reason for discontinuation; and the number and percentage of subjects in each analysis population. By-subject listings will include the date of informed consent, date of screening, date of randomization, date of last visit, date of last contact (if applicable), number of days on study, and reason for discontinuation. Individual subject data for analysis population inclusion and protocol deviations will also be presented in a by-subject listing.

10.3 Demographic and Other Covariates

Subject age will be summarized as mean, standard deviation, median, minimum, and maximum. Sex, race, and ethnicity will be summarized as number and percent of subjects in each category. Subject listings will include age, sex, race, ethnicity, weight, height, and body mass index.

Data listings will also be provided to show prior and concomitant medications, medical history, childbearing potential and pregnancy test results, and general investigator comments. Medication terms will be coded and classified according to the WHO Drug Dictionary, Version B3 (September 2022).

10.4 Dosing Compliance and Extent of Exposure

Descriptive statistics will be used to summarize the total number of applications for the Safety and PK populations. Subjects who apply at least 80% of the expected total number of applications and have no other evidence of material dosing non-compliance will be considered to be compliant with dosing. Duration of treatment (days), number of applications, total weight of product used (g), total diclofenac dose (mg), and average weight per application (g) will be summarized by mean, standard deviation, median, minimum, and maximum.

10.5 Pharmacokinetics Evaluations

Individual plasma diclofenac concentrations will be listed by treatment and time point. These data will be plotted for each individual subject. Generally, the concentration vs time curves may be displayed separately for Day 1 0 to 24 hours, Day 7 0 to 24 hours, and Day 1 to Day 8 (ie, the 24-hour time point for the Day 7 dose) trough levels. Treatments will be overlayed in each of these 3 plots. A similar format will be followed for plots of the treatment means. The concentration data will be summarized for each time point and treatment by mean, standard deviation, median, minimum and maximum. Concentrations reported as below the limit of quantitation (50 pg/mL in the planned assay method) will be included as zero for the purposes of the PK analysis.

The following PK parameters will be calculated for each subject and treatment.

Symbol	CDISC terms	Definition
AUC _{0-τ}	AUCTAU (AUC Over Dosing Interval)	The area under the plasma concentration curve from time 0 to 24 hours calculated by the trapezoidal rule.
C _{max}	CMAX (Max Conc)	The maximum observed plasma concentration in the dosing interval.
C _{min}	CMIN (Min Conc)	The minimum observed plasma concentration in the dosing interval.
PTF	PTROUGH (Peak Trough Ratio)	CMAX/CMIN
T _{max}	TMAX (Time of CMAX)	The (nominal) time of CMAX
T _{min}	TMIN (Time of CMIN Observation)	The (nominal) time of CMIN
λ _z	LAMZ (Lambda z)	The elimination rate constant calculated as the negative of the slope of the log-linear phase of the concentration curve using linear regression
T _½	LAMZHL (Half-Life Lambda z)	Log(2)/LAMZ

The parameters AUC_{0-τ}, C_{max}, and T_{max} will be determined separately for Day 1 and Day 7. All other parameters will be determined for Day 7 only.

Elimination rate constant and half-life will be determined whenever the elimination phase after the Day 7 dose appears to be adequately sampled based on a visual inspection of the log-linear plots.

The parameters $AUC_{0-\tau}$, C_{max} , and C_{min} will be summarized by treatment group as geometric mean and coefficient of variation (calculated as $100*\text{SQRT}(\text{EXP}(\text{VAR}) - 1)$ with VAR = the variance of the log-transformed values), minimum, and maximum. The parameters PTF , T_{max} , T_{min} , λ_z , and $T_{1/2}$ will be summarized by treatment as mean, standard deviation, median, minimum, and maximum.

The log-transformed parameters $AUC_{0-\tau}$ and C_{max} for Day 1 and Day 7 will be compared across treatments using the analysis of variance (ANOVA) model with effects of sequence, subject within sequence, period, and treatment. Sequence will be tested using subject within sequence for error. Period and treatment will be tested against the residual error. Least squares geometric means and standard errors will be provided by treatment. The ratio of geometric means will be determined for Treatments A and B using Treatment C as Reference. A 90% 2-sided confidence interval (ie, two 95% 1-sided tests) will be calculated. The object of the tests is to determine comparability of the rate (C_{max}) and extent ($AUC_{0-\tau}$) of absorption after a single dose and after a week of daily dosing.

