| AST | Aspartate aminotransferase |
| AUC ₀₋₂₄ | Area under the curve for 0-24 hours |
| AUC _t | Area under the plasma concentration-time curve from time zero to time t |
| BUN | Blood urea nitrogen |
| Cav | Average plasma drug concentration |
| CDISC | Clinical Data Interchange Standards Consortium |
| CFR | Code of Federal Regulations |
| CI | Confidence interval |
| CIPT | Cumulative Irritant Patch Test |
| C _{max} | Maximum (peak) plasma drug concentration |
| C _{min} | Minimum plasma drug concentration |
| CMP | Clinical Monitoring Plan |
| COV | Closeout Visit |
| COX | Cyclooxygenase |
| CRO | Contract Research Organization |
| C _{trough} | Concentration of drug reached immediately before the next dose |
| CV | Cardiovascular |
| DDC | Direct data capture |
| DDE | Direct data entry |
| ECG | Electrocardiogram |
| eCRF | electronic Case Report Form |
| EDC | Electronic data capture |
| eICF | Electronic informed consent form |
| EOT | End of treatment |
| ET | Early termination |
| FCBP | Females of child-bearing potential |
| FDA | Food and Drug Administration |
| g | Gram |
| GI | Gastrointestinal |
| GCP | Good Clinical Practice |
| GGT | Gamma-glutamyl transferase |
| GMP | Good Manufacturing Practice |
| HBsAg | Hepatitis B surface antigen |

| | |
|------------------|---|
| HIV | Human immunodeficiency virus |
| ICH | International Conference on Harmonisation |
| IMP | Investigational Medicinal Product (refers to both AMZ001 and Voltaren Arthritis Pain Gel) |
| IMV | Interim Monitoring Visit |
| IRB | Institutional Review Board |
| IUD | Intrauterine device |
| λ_z | Terminal disposition rate constant |
| LC-MS/MS | Liquid chromatography-tandem mass spectrometry |
| MedDRA | Medical Dictionary for Regulatory Activities |
| mg/dL | Milligram per deciliter |
| mL | Milliliter |
| N | Total number of subjects/observations |
| NSAID | Non-steroidal anti-inflammatory drug |
| OA | Osteoarthritis |
| OARSI | Osteoarthritis Research Society International |
| pg | Picograms per milliliter |
| QD | Once daily |
| QID | Four times a day |
| PI | Principal Investigator |
| PK | Pharmacokinetic(s) |
| PKAS | Pharmacokinetic analysis set |
| PTF | Peak-to-trough fluctuation |
| RIPT | Repeat Insult Patch Test |
| SAE | Serious adverse event |
| SAP | Statistical Analysis Plan |
| SDV | Source data verification |
| SIV | Site Initiation Visit |
| SMP | Safety Management Plan |
| SOC | System organ class |
| SOP | Standard Operating Procedure |

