2.2.2 Secondary Endpoint(s)

- The PK parameters C_{max} , minimum plasma drug concentration (C_{min}), time to reach maximum (peak) plasma concentration following drug administration (T_{max}), time to reach minimum plasma concentration following drug administration (T_{min}), terminal disposition rate constant (λ_z), the time it takes for the plasma drug concentration to decrease by half ($T_{1/2}$), average plasma concentration (C_{av}) and peak-to-trough fluctuation (PTF) of the two different dose levels of AMZ001 and one dose level of Voltaren Arthritis Pain Gel will be calculated. The PK parameters for Day 1 will also be calculated and considered as secondary endpoints.

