4.1.2 Exclusion Criteria

The presence of any of the following excludes a subject from study enrollment:

1. Subject has any visible skin disease, skin lesions, wounds, or a significant amount of hair at the application site (knee).
2. Use of an investigational medicinal product (IMP) within 30 days or 5 half-lives (if known), whichever is longer, of enrollment or during the study

3. Treated with systemic or local diclofenac within 30 days of enrollment or during the study (except for study IMP)
4. Known hypersensitivity to diclofenac, any excipients (ethanol, propylene glycol, diethylene glycol monoethyl ether, myristyl alcohol, hydroxypropyl cellulose, and water), aspirin, Xarelto, coumadin, or other NSAIDs, including Cyclooxygenase-2 (COX-2) inhibitors
5. Any history of drug hypersensitivity, asthma, urticaria, or other significant allergic diathesis. Subjects with uncomplicated seasonal allergic rhinitis can be accepted only if expected allergy season is clearly outside enrolment/ treatment periods.
6. Females who are pregnant and/or lactating
7. Of child-bearing potential but not willing to use adequate contraception for the duration of the study
8. Subject is a current smoker and unable to abstain from smoking during the treatment periods.
9. Use of any topical medication, cosmetics, cream, ointments, lotions on the treatment site 1 week prior to enrollment through EOT visit.
10. Use of any medication (including over-the-counter medication, dietary supplements, and herbal remedies) within 2 weeks before first scheduled study drug administration or within less than 5 times the elimination half-life of the respective drug (whichever is longer) or is anticipated to require concomitant medication during the 2-week period or at any time throughout the study. Consumption of any drug metabolizing enzyme (e.g., cytochrome P450 3A4 (CYP3A4) or other cytochrome P450 enzymes) inducing or inhibiting beverages or food (e.g., broccoli, Brussels sprouts, grapefruit, grapefruit juice, star fruit) within 3 days prior to and during each treatment period.

Allowed treatments are:

- Systemic contraceptives and hormone replacement therapy, as long as female subject is on stable treatment for at least 3 months and continues treatment throughout the study.
 - Occasional use of acetaminophen 500 mg (up to 1000 mg daily)

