9.7.2 Pharmacokinetics (PK)

PK analysis will be performed using the SAS® system. PK parameters assessed at Day 1 and Day 7 will include $AUC_{0-\tau}$, C_{max} , C_{min} , C_{av} , PTF, T_{max} , T_{min} , λ_z , and $T_{1/2}$, and will be presented in listings for individual subjects and summarized in tables and figures.

PK parameters $AUC_{0-\tau}$ and C_{max} will be compared across treatment groups using an analysis of variance (ANOVA) model. The ratio of the PK parameters will be estimated along with 90% confidence limits to assess comparable bioavailability.

Please refer to the SAP for detailed analysis method.

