9.7.4 Secondary Endpoint(s)

The PK parameters C_{max} , C_{min} , T_{max} , T_{min} , λ_z , $T_{1/2}$, C_{av} and PTF of the two different dose levels of AMZ001 and the one dose level of Voltaren Arthritis Pain Gel will be calculated. The PK parameters for Day 1 will also be calculated and considered as secondary endpoints.

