3. STUDY DESIGN

The study will follow a randomized open-label 3-way crossover design in which every subject will receive all 3 study products in one of the 6 possible treatment sequences. During each of the 3 study periods, subjects will receive daily treatment for 7 successive days. Subjects will be confined to the study site under supervision from the evening before the first treatment application of the period until 24 hours after the last application. The treatment periods will be separated by 2 washout periods of 21 days each.

Treatments and treatment sequences are defined as follows.

Sequence Number	Period 1	Period 2	Period 3
1	A	B	C
2	B	C	A
3	C	A	B
4	B	A	C
5	A	C	B
6	C	B	A

Treatment A: 6 mL (5.5 g) daily, 2 doses of 1.5 mL on each knee QD

Treatment B: 8 mL (7.4 g) daily, 4 doses of 1 mL on each knee QD

Treatment C: Voltaren Arthritis Pain Gel, 32 g daily, 4 g on each knee 4 times daily

At each application, subjects will spread the gel directly to pre-defined treatment areas of approximately 400 cm² (Treatments A and C) and 500 cm² (Treatment B) on each knee following prescribed application instructions.

On Day 1 and Day 7, blood samples for PK analyses will be collected within 1 hour prior to application and at 2, 4, 6, 8, 10, 12, 14, 16, 18, 20, and 24 hours after application. Trough level samples will be collected before application on Days 3, 4, 5, and 6. At the end of Period 3, additional PK blood samples will be taken at 3, 4, and 5 weeks after the last application in order to characterize and to compare the elimination kinetics of the 3 study products.

Subjects will be healthy males or females 18 to 65 years old, determined by the Investigator to be in good general health based on medical history and physical examination, including vital signs, 12-lead ECG, and clinical laboratory tests. Approximately 75 subjects will be randomized to ensure at least 60 evaluable subjects.

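### SAP 10.5 departs from the protocol's secondary PK endpoints without declaring it, and its BLQ-equals-zero rule can make the planned Cmin and PTF summaries uncomputable

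*SAP*

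**What the plan says.** **Protocol.** The synopsis and section 2.2.2 list the secondary PK endpoints, including "average plasma concentration (C_{av}) and peak-to-trough fluctuation (PTF". Section 9.7.4 repeats the list and adds: "The PK parameters for Day 1 will also be calculated and considered as secondary endpoints". Section 9.7.2 opens "PK parameters assessed at Day 1 and Day 7 will include" and then names AUC0-τ, Cmax, Cmin, Cav, PTF, Tmax, Tmin, λz and T½. It ends "Please refer to the SAP for detailed analysis method". No formula for PTF appears anywhere in the protocol.

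**SAP 10.5.** The parameter table has eight rows: AUC0-τ, Cmax, Cmin, PTF, Tmax, Tmin, λz and T½. PTF carries the CDISC term "PTROUGH (Peak Trough Ratio" and the definition Cmax divided by Cmin. Only AUC0-τ, Cmax and Tmax are derived on Day 1; everything else is for Day 7 alone. Concentrations below 50 pg/mL enter the PK analysis as zero. Cmin is the lowest observed concentration in the dosing interval. Cmin is summarized by geometric mean and by a CV built from the variance of the logged values. PTF is summarized by mean, SD, median, minimum and maximum.

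**SAP 11.** Despite its heading on changes from the protocol, this is one sentence promising that departures from the SAP's own analyses will be explained in the study report.

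**The concern.** There are two separate problems.

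First, a report that follows the SAP exactly would leave out one listed endpoint (Cav), show a ratio under the symbol the protocol uses for a fluctuation, and lack most of the Day 1 parameters. Because SAP 11 covers only departures from the SAP, nothing would prompt the report to disclose any of this.

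Second, the BLQ rule, the Cmin definition and the log-scale summary do not fit together. If a Day 7 sample is BLQ, the analyst must choose after seeing the data, in an open-label study, whether to drop the zero, substitute a value or change the statistic. Cmin and fluctuation describe how a once-daily and a four-times-daily regimen differ within the day, so an unplanned choice there could colour the comparison if BLQ troughs were uneven between treatments.

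**Working it through.** **Step 1: protocol against SAP**

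| Parameter | Protocol 9.7.2 | SAP 10.5 |
|---|---|---|
| AUC0-τ, Cmax, Tmax | Day 1 and Day 7 | Day 1 and Day 7 |
| Cmin, Tmin, λz, T½ | Day 1 and Day 7 | Day 7 only |
| PTF | Day 1 and Day 7, expanded as fluctuation, no formula | Day 7 only, Cmax/Cmin, termed a ratio |
| Cav | Day 1 and Day 7 | absent |

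So one endpoint is missing, one is relabelled, and five parameters (Cmin, Tmin, PTF, λz, T½) lose Day 1. None of this is declared in SAP 11.

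**Step 2: the SAP formulas with one BLQ value**

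Samples per Day 7 profile (SAP 3): pre-dose, ten samples from 2 to 20 h at two-hour steps, and 24 h, so 1 + 10 + 1 = 12. If any one counted in the interval is BLQ:

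- Cmin = 0.
- Cmax/Cmin is a division by zero, so the treatment mean and SD of PTF do not exist.
- log(Cmin) = log(0) does not exist, so neither does the mean of the logs.
- CV = 100·√(exp(VAR) − 1) needs the variance of the logs, which also does not exist.

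One such subject is enough to affect the whole treatment column. SAP 8 (no imputation of missing values) does not help, because the zero is an assigned value and not a missing one.

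By contrast, 100·(Cmax − Cmin)/Cav at Cmin = 0 becomes 100·Cmax/Cav, which is finite whenever Cav > 0.

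**Step 3: does the unplanned choice matter?**

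Illustration on assumed data, since the documents give no concentrations: one simulated set of 60 lognormal Cmin values (median 300 pg/mL, log SD 0.6), with the lowest k declared BLQ. Two repairs an analyst might pick, neither of them in the SAP:

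| k BLQ of 60 | Zeros dropped: geometric mean, CV | LLOQ/2 = 25 pg/mL: geometric mean, CV |
|---|---|---|
| 1 | 299, 51% | 287, 63% |
| 3 | 311, 47% | 274, 80% |
| 6 | 325, 44% | 251, 106% |

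At k = 1 the geometric means differ by about 4% (299/287 = 1.04); at k = 6 by about 29% (325/251 = 1.29). The CV is more sensitive than the mean.

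**Step 4: how likely is it?**

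The documents do not say. If p is the chance that a subject's Day 7 profile contains a BLQ value, independent between 60 subjects on a treatment, the chance of at least one is 1 − (1 − p)^60:

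| assumed p | 0.5% | 1% | 2% | 5% | 10% |
|---|---|---|---|---|---|
| at least one in 60 | 26% | 45% | 70% | 95% | 99.8% |

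These are conditional figures. The true p may be close to zero: Day 7 follows six days of dosing, and the planned samples at 21, 28 and 35 days suggest that measurable drug was thought possible long after the last application.

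**Step 5: the Day 1 restriction**

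Protocol 4.1.2 excludes a subject "Treated with systemic or local diclofenac within 30 days of enrollment or during the study (except for study IMP", so the Period 1, Day 1 pre-dose sample should be BLQ. SAP 3 says "blood samples for PK analyses will be collected within 1 hour prior to application", but SAP 10.5 does not say whether that sample belongs to the interval for Cmin. If it does, Day 1 Cmin in Period 1 is expected to be zero. That could be a sound reason for the Day 7 restriction, but the SAP does not give it.

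**The case against.** The strongest reply has four parts.

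- *The protocol leaves the method to the SAP.* This holds for the choice of a PTF formula. A reader might infer that the SAP contradicts a protocol formula, but there is none; the documents show only *fluctuation* in one and *ratio* in the other. The SAP also prints its formula openly, so nobody would be misled about the number. Referring the method to the SAP does not, however, cover omitting a listed endpoint or the Day 1 values that the same section lists.
- *Cav adds nothing.* Correct in substance: it equals AUC0-24/24, and AUC is summarized. It is still a named endpoint without a row.
- *BLQ on Day 7 may never occur, and a geometric mean taken as a product would be 0 instead of undefined.* The first part stands: the frequency is unknown. The second part rescues only the mean. The log-scale CV and the ratio still fail. The median of PTF could be kept by a convention for the undefined value, but the SAP states none.
- *Restricting to Day 7 is sensible.* Perhaps so. A reader might infer from the expected BLQ pre-dose sample that Day 1 output will fail throughout Period 1. It will not: the SAP plans no Day 1 Cmin or PTF, so no planned output is affected. What remains is that the restriction is undeclared.

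A reader might also want to say by how many percentage points the ratio misstates fluctuation. The documents cannot support that, because the relation between Cmax/Cmin and (Cmax − Cmin)/Cav depends on the shape of the profile, and no profile is given.

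**Conclusion.** The point holds as an inconsistency between protocol and SAP plus a missing analysis rule. The mismatches on Cav, PTF and Day 1 are certain from the text and stand even if no Day 7 sample is ever BLQ. The failure of the Cmin and PTF summaries is certain once one Day 7 value in the interval is BLQ, but its likelihood cannot be determined; the figures in steps 3 and 4 rest entirely on assumed values.

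The reach is limited. A reader might infer that the bioavailability conclusion is at risk. It is not: the Day 7 AUC0-τ and Cmax comparison uses neither Cmin nor PTF, a zero enters the trapezoidal AUC without difficulty, and log(Cmax) would fail only if every sample in a profile were BLQ. BLQ values also remain visible in the concentration listings. This is a modest correction to descriptive secondary endpoints, best made before database lock.

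**What to change.** In SAP 10.5:

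1. Add Cav = AUC0-24/24.
2. Define PTF as a fluctuation, for example 100·(Cmax − Cmin)/Cav, which stays finite at Cmin = 0 when Cav > 0. If Cmax/Cmin is kept, report it under its own name with the number of undefined values.
3. Summarize Cmin the same way for all three treatments: median, minimum and maximum with zeros kept, plus the number of BLQ values. Give a geometric mean and CV only if no Cmin is BLQ in any treatment, so that the columns stay comparable.
4. State whether the pre-dose sample counts towards Cmin.

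In SAP 11, declare the Day 7 restriction with its reason. Alternatively, derive those Day 1 parameters that can be estimated.

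Items 1 to 4 and a declaration cost a few lines of SAP text and code and need no new data, because AUC, Cmax and Cmin are already derived for Day 7. Deriving Day 1 parameters costs more, particularly λz: it would need the visual inspection step again, and with the protocol's example application times (last application 15 h after the first) only the 16, 18, 20 and 24 h samples follow the last Voltaren application.

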Secondary endpoint(s):

- The PK parameters C_{max} , minimum plasma drug concentration (C_{min}), time to reach maximum (peak) plasma concentration following drug administration (T_{max}), time to reach minimum plasma concentration following drug administration (T_{min}), terminal disposition rate constant (λ_z), the time it takes for the plasma drug concentration to decrease by half ($T_{1/2}$), average plasma drug concentration (C_{av}) and peak-to-trough fluctuation (PTF) of the two different dose levels of AMZ001 and one dose of Voltaren Arthritis Pain Gel will be calculated. The PK parameters for Day 1 will also be calculated and considered as secondary endpoints.

Safety endpoint(s):

- Adverse Events (AEs); including serious, treatment emergent, adverse drug reactions (ADRs)
- Local and systemic tolerability

STATISTICAL METHODS:

Below is a summary of the statistical analysis methods. For more details on each analysis, please refer to [Section 9](#).

Sample Size: Based on the assumption (averaging historical data and 000084 result), intra-subject coefficient of variation (CV) was 61%. A total of sixty (60) evaluable subjects will achieve 80% power using 95% confidence interval (CI), to account for multiplicity. The true ratio that was used in the sample size calculation was 1.05. Enough healthy adults will be screened to randomize approximately seventy-five (75) subjects to ensure sixty (60) evaluable subjects, assuming a 20% dropout and non-evaluable rate. All subjects will receive all 3 treatments over the course of the 3 study periods. Subjects will be randomized to one of the 6 possible sequences of 3 treatments, as specified in the design section above, to provide adequate information about the PK parameters and safety for the purposes of this study.

Statistical analysis: Descriptive statistics will be used to summarize the baseline demographic information.

Safety analysis: Descriptive statistics will be used to summarize AEs, laboratory data, physical examinations, and vital signs.

Pharmacokinetic (PK) Analysis: PK analysis will be performed using SAS® system.

PK parameters area under the plasma concentration-time curve from time zero to time t ($AUC_{0-\tau}$) and C_{max} will be compared across treatment groups using an analysis of variance (ANOVA) model. The ratio of the PK parameters will be estimated along with 90% confidence limits to assess comparable bioavailability.

SIGNATURE PAGE

AMZ001 (Diclofenac Sodium Gel 3.06%)

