9.1 Determination of Sample Size

Based on the assumption (averaging historical data and Phase 1 Study 000084 study results), intra-subject coefficient of variation (CV) was 61%. A total of sixty (60) evaluable subjects will achieve 80% power using 95% confidence interval (CI), to account for multiplicity. The true ratio that was used in the sample size calculation was 1.05. Enough healthy adults will be screened to randomize approximately seventy-five (75) subjects to ensure sixty (60) evaluable subjects, assuming a 20% dropout and non-evaluable rate. All subjects will receive all 3 treatments over the course of the 3 study periods. Subjects will be randomized to one of the 6 possible sequences of 3 treatments, as specified in the design in [Figure 1](#), to provide adequate information about the PK parameters and safety for the purposes of this study.

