7. SAMPLE SIZE DETERMINATION

The sample size of 60 subjects was determined to provide 80% power in a standard two 1-sided test of bioequivalence assuming an intrasubject coefficient of variation (CV) of 61% and a true

ratio of geometric means 1.05. These assumptions were derived by averaging historical data and the results of Study 000084. For the purposes of the sample size estimate, bioequivalence was defined as the inclusion of a 2-sided 95% confidence interval (1-sided 97.5%) on the ratio of geometric means (Test/Reference) within the equivalence margin of 80% to 125%. The wider confidence interval was used to account for the multiplicity of tests planned in the study. The plan to enroll 75 subjects assumes that 20% of enrolled subjects will be incomplete or not evaluable.

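### The trial is sized on a 95% confidence interval for multiplicity but analysed with an unadjusted 90% interval and no written pass rule; separately, the stated 80% power follows from neither level

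*SAP*

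**What the plan says.** **Sizing.** SAP 7: "For the purposes of the sample size estimate, bioequivalence was defined as the inclusion of a 2-sided 95% confidence interval" lying within 80% to 125%. The reason given is "The wider confidence interval was used to account for the multiplicity of tests planned in the study". Protocol 9.1 and the synopsis agree on the level and the reason, claiming "80% power using 95% confidence interval (CI), to account for multiplicity" for 60 evaluable subjects, but give no limits. All three use an intra-subject CV of 61% and a true ratio of 1.05.

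**Analysis.** SAP 10.5 compares Treatments A and B with Treatment C for AUC over 24 hours and Cmax, on Day 1 and Day 7: "A 90% 2-sided confidence interval (ie, two 95% 1-sided tests) will be calculated". Protocol 9.7.2 and the synopsis PK paragraph agree: "The ratio of the PK parameters will be estimated along with 90% confidence limits to assess comparable bioavailability". None of these passages has an adjustment, a testing order or acceptance limits.

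**Decision.** Protocol 9.7.2 defers to the SAP ("Please refer to the SAP for detailed analysis method"). SAP 10.5 gives only a purpose: "The object of the tests is to determine comparability of the rate" (Cmax) and extent (AUC) of absorption. Protocol 2.2.1 makes Day 7 AUC0-24 and Cmax primary, and 2.2.2 makes Day 1 secondary. Protocol 3.5.4 says the aim is to settle on one AMZ001 dose. SAP 11 does not mention the two confidence levels.

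**The concern.** The sample-size sections tell the reader that the wider interval deals with multiplicity. The analysis sections do not use that interval and put nothing in its place.

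A comparability call will be made on two doses and two parameters, because the doses were chosen to match the reference and one is to be selected. The limits are confined to the sizing calculation and the pass rule is unwritten, so that call is not fixed before results are seen. The level matters: an observed ratio of 1.03, for example, would meet 80-125% at 90% and miss it at 95%.

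Checking which test the 80% power belongs to exposes a second defect: it belongs to neither.

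**Working it through.** **Inputs.** N = 60 evaluable, CV = 0.61, true ratio 1.05 (SAP 7, Protocol 9.1); limits 0.80-1.25 (SAP 7); three-treatment, three-period crossover in which every subject receives all treatments (SAP 3). I assume complete, balanced data.

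**Standard error**
- Within-subject log SD = sqrt(ln(1 + 0.61²)) = sqrt(0.3163) = 0.5624
- SE of a log ratio = 0.5624 × sqrt(2/60) = 0.1027
- Residual df = 2×60 − 4 = 116

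**Reproducing the plan's figures.** Dropout inflation is correct: 60/(1 − 0.20) = 75. The power is not reproduced. The table gives two one-sided tests, integrated over the distribution of the residual variance, per parameter and per comparison. The passing window is exp(ln 0.80 + h) to exp(ln 1.25 − h), where h is the half-width and ln 1.25 = 0.2231.

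| | 95% interval | 90% interval |
|---|---|---|
| t (116 df) | 1.981 | 1.658 |
| Half-width h = t × SE | 0.2034 | 0.1703 |
| Observed ratios that pass | 0.980-1.020 | 0.948-1.054 |
| Power, ratio 1.05, N = 60 | 14.1% | 35.6% |
| Evaluable N for 80% power | 168 | 134 |
| CV giving 80% power at N = 60 | about 34% | about 39% |

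The gap, 35.6% − 14.1% = about 21%, is the chance that the two levels give different answers on one comparison at ratio 1.05. Part of it reflects the high CV; at CV 34% the gap is about 8 points.

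Using two-period degrees of freedom (58) gives 13.8% and 34.8%. Of the limits tried, the stated N came back only with wider ones: 70-143% at the 95% level gives N = 58, and 81.9% power at 60. The documents do not state such limits.

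**False equivalence, either dose declared comparable** (simulation, N = 60, CV 61%, shared reference arm). In the first row exposure is proportional to dose (0.60/0.80 = 6/8), with the higher dose on the lower limit.

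| True ratios (A, B) | One pre-named parameter, 90% | One pre-named parameter, 95% | Both parameters required, 90% |
|---|---|---|---|
| 0.60, 0.80 | 4.7% | 1.6% | 1.5-2.7% |
| 1.25, 1.25 | 8.3% | 3.0% | 2.8-4.9% |
| 0.80, 1.25 | 9.2% | 3.2% | 3.0-5.3% |

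The last column assumes a correlation of 0.7 to 0.9 between log AUC and log Cmax, which the documents do not give. The third row is remote: it needs a 1.56-fold exposure gap (1.25/0.80) for a 1.33-fold dose gap (8/6).

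**Power per dose with both parameters required** (same correlations, ratio 1.05, N = 60): 3.5-5.8% at 95% and 18-24% at 90%. For 80%, about 187-200 or 151-162 evaluable subjects are needed.

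**The case against.** - **The 90% level is deliberate.** All three analysis passages agree on it, and SAP 7 confines the 95% definition to sizing. A stricter level used only for sizing could be a power allowance for several tests that must all pass. The documents do not say which purpose was meant. A reader might infer that an error-rate adjustment was planned and then dropped; the text supports only that the difference is unexplained.
- **Limits exist.** SAP 10.5 plans two one-sided tests, these need limits, and 80-125% is the only pair in the documents. So the plan does not lack limits altogether. What stands is that SAP 7 restricts them to the sample-size estimate and no analysis passage adopts them.
- **Inflation is small on the natural reading.** SAP 10.5 names rate and extent together, which points to requiring both parameters, and the 90% interval then gives at most about 5%. This is right as far as it goes, but the requirement is not written.
- **The aim is to characterise, not to claim bioequivalence.** The wording is indeed mild. But the plan speaks of tests and sizes them for bioequivalence, and one dose is to be identified, so a criterion will be applied in practice.

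**Conclusion.** The inconsistency is real and should be fixed. The level used for sizing differs without explanation from the level used for analysis, and the limits and pass rule are missing from the analysis sections.

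The consequence for error control is modest. The 8-9% rates need success on a single pre-named parameter by either dose, with both true ratios exactly on a limit. With exposure proportional to dose there is no inflation above 5%, and with both parameters required the ceiling is about 5%.

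A reader might infer that 80% is correct for the 95% test and is lost by analysing at 90%. The plan's own inputs contradict this: power is about 14% at 95% and rises to about 36% at 90%. The shortfall is a separate defect, already present, and larger in size.

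These figures assume that the 61% CV applies on the log scale to the parameter tested (the documents do not say whether it is for AUC or Cmax). The both-parameter figures also depend on the assumed correlation.

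**What to change.** Write one rule, identically, into SAP 10.5, Protocol 9.7.2 and the synopsis:

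- acceptance limits of 80-125% as in SAP 7, unless the sponsor shows that the sizing used others;
- Day 7 AUC0-24 and Day 7 Cmax as the deciding parameters, with Day 1 secondary;
- each AMZ001 dose assessed against Treatment C, with both parameters required for a dose;
- one confidence level.

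For the level, the sponsor chooses and justifies one option:
1. Carry the 95% interval into the analysis, with 90% intervals descriptive.
2. Keep the 90% interval, delete the multiplicity wording from SAP 7, Protocol 9.1 and the synopsis, and justify making no adjustment across the two doses.

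In either case, reconcile CV, limits and N, and replace the power sentence with the figure that the chosen rule delivers at 60 evaluable subjects.

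This should be done before any concentration results by treatment are released. Database lock is too late: the bioanalytical laboratory is blinded, but the trial is otherwise open-label (Protocol 3.5.3).

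Cost: a written protocol amendment under Protocol 11.1, with IRB approval if it is judged to affect scientific quality significantly, and a much less favourable stated power. Option 1 with both parameters required leaves very little power at N = 60, and the sponsor should see that before choosing. The rule itself needs no new data, procedures or subjects.
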